Hybrid Effectiveness-Implementation Study to Improve Clopidogrel Adherence

NCT01609842

STUDY PROTOCOL AND STATISTICAL ANALYSIS PLAN

Document Date: February 26, 2019

Uploaded: 05/06/2019

Protocol

Project Title: Hybrid Effectiveness-Implementation Study to Improve Clopidogrel Adherence

Principal Investigator: P. [name], PhD

I. Hypotheses and Specific Aims

Clopidogrel is a critical therapy following percutaneous coronary intervention (PCI) with stent placement and reduces the risk of stent thrombosis, myocardial infarction (MI) and mortality (1-7). Despite the importance of clopidogrel following stent implantation, multiple VA and non-VA studies have demonstrated adherence gaps to clopidogrel, both delays in initial filling of the medication at hospital discharge (~16%) and early discontinuation during longitudinal use (up to 30%). These studies demonstrate clear evidence and guideline consensus supporting clopidogrel adherence, adverse consequences of non-adherence, and the care gap that will be the focus of this project.

Non-adherence to clopidogrel is common in the VA. From the VA's Cardiovascular Assessment Reporting and Tracking in the Cardiac Catheterization Laboratory (CART-CL), we found that 22.4% of patients delayed filling clopidogrel following PCI in FY09 with delay defined as filling a clopidogrel prescription > 1 day after discharge. Further, approximately 1/3 of patients discontinued clopidogrel early (< 9 months) prior to the recommended one year treatment duration. Even among patients without an initial delay in clopidogrel filling, almost 40% of patients discontinued clopidogrel by 9 months of hospital discharge. At the hospital level, there is also significant variation in clopidogrel non-adherence. On average at each PCI facility, 18.9% of patients delay filling clopidogrel, and 30-40% discontinue clopidogrel early by 9 months. These findings highlight significant opportunities to improve clopidogrel adherence following stent implantation in the VA.

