Overview: This four-year multi-site site-level randomized stepped wedge trial will test the effectiveness of the intervention to improve adherence and outcomes, and will formatively evaluate and refine the implementation process. This is a randomized stepped-wedge study, modified to allow stratification by clopidogrel adherence. We will randomize 16 VA PCI sites to the multi-faceted intervention through 4 roll-out phases. We will implement the intervention at 4 sites during each roll-out and incorporate a 6-month delay between the start of each roll-out. The rest of the PCI sites that are not randomized will serve as usual care control group. At each site, we will enroll patients over a 6-month period and follow them for 12 months following PCI. The multi-faceted intervention will adapt elements of prior successful intervention and will include the following core components: development of a software application integrated within CART-CL that assessed whether patients fill their clopidogrel prescription at hospital discharge, collaboration between cath lab clinicians and inpatient/outpatient pharmacy teams, patient education, and tele-monitoring via IVR technology.

A. Outcome Measure(s):

Initial outcomes will assess understanding current practices as VA PCI facilities to enhance adherence to clopidogrel. We will then assess barriers and facilitators to intervention implementation during each roll-out phase through semi-structured interviews and incorporate lessons learned from each roll-out phase into subsequent roll-out phases.

The primary outcomes of the study include the proportion of patients whose clopidogrel prescription is filled at hospital discharge following the PCI stent placement as well as the proportion of patients who are adherent based on the pharmacy refill data in the year after hospital discharge. Secondary outcomes include hospitalizations for bleeding, myocardial infarction, stroke, and mortality. Additionally, data about the costs of the intervention will be collected to assess the cost-effectiveness of the intervention.

B. Description of Population to be Enrolled:

Setting, sites, and patients:

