Quantitative analyses: The primary analysis will use patient level data and generalized linear mixed models. These models can accommodate the different types of outcomes, correlation due to clustering of patients within sites, and different numbers of patients across sites and time periods (43). Models will include terms for site (random, to account for correlation of patients within sites and to identify site-level variables), roll-out period (fixed, to avoid confounding of intervention with time trends), stratum (fixed, to account for baseline clopidogrel adherence quartile), and intervention variable (fixed, INT/UC, the effect of interest). The availability of non-intervention usual care control sites provides additional information for estimating the intervention effect, and also will allow us to examine possible dependence of the intervention effect on baseline clopidogrel adherence. These latter analyses for interaction between intervention and baseline adherence will be considered exploratory. Primary yes/no outcomes (clopidogrel fill, bleeding, stroke, MI, mortality) will be analyzed with mixed logistic regression models with these methods. The clopidogrel adherence outcome is a numeric percentage and will be analyzed

with similar models for normal outcomes, using transformations as needed to achieve approximate normality.

Available data for analysis will include clopidogrel fill and adherence data at each site during the 6 month period preceding the first roll-out, and during each of the four subsequent 6 month roll-out periods of the study, and outcomes (mortality, bleeding, stroke, and MI) during the 12 months following the index PCI procedure. Data will be examined graphically and descriptively for general patterns, outliers, or other problems. Descriptive tables will show general patterns and trends in site and average patient characteristics and outcomes, separately for sites under usual care (UC) and those under intervention (INT), and by time periods.

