Hybrid Effectiveness-Implementation Study to Improve Clopidogrel Adherence

NCT01609842

ADDENDUM TO STATISTICAL ANALYSIS PLAN

Document Date: May 1, 2019

Uploaded: 05/06/2019

We have made the following additions and clarifications to the original Statistical Analysis plan (described in the study protocol):

- 1. In addition to the intervention group of patients who were treated during the 6 month intervention period, we consider three control groups: a) patients who were treated at a site before the intervention was applied there, b) patients who were treated at a site after the intervention was ended there, and c) patients who were treated at a site that was eligible but at which the intervention was never applied. The primary hypothesis is intervention versus pre-intervention, and other comparisons are considered secondary analyses.
- 2. We used mixed logistic regression models for clopidogrel adherence (y/n PDC > 80%) as planned. To express results on a more interpretable risk difference scale we used standardized or average predicted value estimators (e.g. Zou, 2009; Joffe and Greenland, 1995), which compare probabilities of adherence among the groups, hypothesizing (in some cases counterfactually) that patients were in each of the four intervention/control groups. Inference was carried out using bootstrap methods and results expressed as confidence intervals for differences between groups. The same methods were used to express survival probabilities and differences in more interpretable terms (Sjolander, 2016).
- 3. Sensitivity analyses were carried out removing patients who received bare metal stents.

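### The addendum calls the logistic PDC > 80% analysis of adherence planned, but the only model the protocol names for adherence is a normal-outcome model of a percentage, and the protocol gives no cut-off

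*SAP*

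**What the plan says.** Adherence is one of two primary outcomes (Protocol, Specific Aims, Aim 4). The protocol describes it in two places.

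- **IV.A, Outcome Measure(s):** the outcome is "the proportion of patients who are adherent based on the pharmacy refill data in the year after hospital discharge". This implies that each patient is classed as adherent or not. No adherence measure, cut-off or model is given.
- **IV.F, Quantitative analyses:** logistic models are assigned by a list: "Primary yes/no outcomes (clopidogrel fill, bleeding, stroke, MI, mortality) will be analyzed with mixed logistic regression models with these methods". Adherence comes next and is handled separately, as a numeric percentage, to be modelled "with similar models for normal outcomes, using transformations as needed to achieve approximate normality".

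The SAP addendum says that it makes "additions and clarifications to the original Statistical Analysis plan (described in the study protocol"), so the protocol is the plan it refers to. Item 2 then states: "We used mixed logistic regression models for clopidogrel adherence (y/n PDC > 80%) as planned". It goes on to describe standardised risk differences and says: "Inference was carried out using bootstrap methods and results expressed as confidence intervals for differences between groups". It does not mention the numeric-percentage analysis.

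**The concern.** A reader who meets the logistic PDC > 80% result will take it as the pre-specified analysis of a primary outcome, because the addendum says so. If the protocol actually specified another outcome type and model, and no cut-off, that reader is misinformed on the point that decides how much weight the result can bear. Dichotomising a refill percentage involves two choices: to dichotomise at all, and where to cut. When neither is documented before the analysis, a reader cannot tell whether they were made independently of the results. Telling the reader that the plan was followed also removes the reason to check.

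**Working it through.** The plan states no figure to reproduce. The check is a comparison of texts, followed by one illustrative calculation.

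**1. Outcome type, model and cut-off**

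| Element | Protocol IV.A | Protocol IV.F | Addendum item 2 |
|---|---|---|---|
| Form of adherence | yes/no per patient (implied) | numeric percentage | yes/no |
| Measure | refill data, not defined | percentage, not named | PDC |
| Cut-off | none | none needed | > 80% |
| Model | none | mixed model for normal outcomes, transformed as needed | mixed logistic |

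- *Form:* the addendum agrees with IV.A and disagrees with IV.F.
- *Model:* IV.F is the only place with a model for adherence, and the addendum's model is not that one. The item on clopidogrel fill in the logistic list does not cover adherence: filling at discharge and later adherence are separate primary outcomes in Aim 4 and IV.A.
- *Measure:* IV.F already planned a percentage, and IV.D and the description of the IVR calls provide for fill dates and supply. A refill-based percentage is therefore not new; only its name is.
- *Cut-off:* no adherence threshold appears in the protocol. Its only 80% figure is a response rate for email surveys (Aim 1, Steps 4 and 5).

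**2. Timing**

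The addendum reports completed work: models were used and inference was carried out. Nothing in either document states when the yes/no form or the 80% cut-off was settled relative to data access.

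**3. Illustration of what freedom between the two forms could do**

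Assumptions, none from the documents: no true effect, two-sided 5% tests, independent patients, and a rule of claiming success if either form is significant. Under the null the two test statistics are approximately bivariate normal, with correlation r equal to the correlation between PDC and the indicator PDC > 0.8. Then

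P(either significant) = 1 − P(|Z1| ≤ 1.96 and |Z2| ≤ 1.96).

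The limits are 5% at r = 1 and 1 − 0.95² = 9.75% at r = 0.

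Worked case, PDC distributed as beta(2,1), density 2x:
- share above 0.8 = 1 − 0.8² = 0.36
- mean = 2/3, variance = 1/18
- covariance with the indicator = (2/3)(1 − 0.8³) − (2/3)(0.36) = 0.3253 − 0.2400 = 0.0853
- r = 0.0853 / √[(1/18)(0.36 × 0.64)] = 0.0853 / 0.1131 = 0.754
- P(either significant) = 8.07%

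Across 13 assumed shapes (36% to 74% of patients above 80%), r for untransformed PDC runs from 0.754 to 0.876, and the false-positive chance from 8.07% down to 7.25%: about 7.3% to 8.1%.

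**The case against.** The best defence is that the addendum follows the protocol's stated endpoint. IV.A asks for a proportion of adherent patients, a mixed logistic model is the natural choice for that, and IV.F opens by planning generalized linear mixed models for outcomes of different types. A refill percentage was already foreseen, and an addendum that announces additions and clarifications is a proper place to supply a missing cut-off.

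Much of this stands. The yes/no form has a basis in the protocol, and supplying a threshold is legitimate if it is declared as an addition. What does not stand is the description. IV.A names no model, and the general opening of IV.F is followed by a specific assignment for adherence that the addendum does not follow. A cut-off that the plan never contained cannot have been applied according to that plan. The addendum had the chance to state and resolve the conflict between IV.A and IV.F, and passes over it.

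Two stronger readings are tempting. The first is that the form or cut-off was chosen because it gave a better result. The documents do not support this: nothing shows that another form or threshold was tried. The second is that the interval between the protocol ("Document Date: February 26, 2019") and the addendum (May 1, 2019) shows a late choice. It does not. These are document dates; the protocol is written in the future tense and cites web pages accessed in 2011, so its date need not be when its text was written, and the interval does not date the decision. Only the past tense of the addendum bears on timing, and it shows just that the cut-off is first documented after the analysis was done.

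**Conclusion.** The concern holds as a false statement about pre-specification of a primary analysis. The claim to have followed the plan is wrong for the model, unsupported for the 80% cut-off, and defensible only for the yes/no form. Behind it lies an unresolved inconsistency in the protocol between IV.A and IV.F. This rests on the text alone and on no assumption.

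The effect on this trial's results cannot be sized from the documents. The 7.3% to 8.1% describes a hypothetical free choice between two forms under assumed PDC shapes. It shows why disclosure matters and is not evidence about this trial.

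**What to change.** 1. In addendum item 2, replace the claim that the analysis was planned with a statement that IV.A and IV.F of the protocol conflict; that the logistic PDC > 80% analysis takes the yes/no form of IV.A and departs from the model in IV.F; and when, relative to data access, and why the 80% cut-off was chosen.
2. Report the numeric-percentage mixed model of IV.F alongside it, whatever its result, in the same patients and for the same intervention versus pre-intervention contrast. State any transformation used, since IV.F leaves that to be decided from the data.

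The numeric model compares mean percentages and so answers a different question. It restores the analysis that the protocol promised but does not test how far the binary result depends on 80%; that would need other cut-offs.

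The cost is a change of wording and one further model on data already held. The downsides are a less favourable account of pre-specification and possibly two adherence results that differ and must be explained.
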